9.6. Biomarkers

Archived formalin-fixed paraffin-embedded tumor or fresh lymph node biopsy (if collection is feasible and where local regulations and shipping logistics permit) will be used for biomarker evaluations at Screening and at the time of disease progression. If archived tissue is unavailable and a fresh lymph node biopsy cannot be obtained, bone marrow biopsy slides (when positive for disease) can be used.

In the event that no archived tissue is available, the subject is too unstable to undergo a fresh biopsy, but it is expected that the biopsy may be feasible after beginning chemotherapy, a fresh lymph node biopsy is recommended to be obtained after debulking with the study treatment regimen in subjects with DLBCL only (cell of origin studies will not be affected by initiation of therapy). Blood samples for biomarker evaluations, as described in Section [3.2.6](#), will be collected according to the Time and Events Schedule ([Table 1](#), [Table 2](#), [Table 3](#), and [Table 4](#)).

Stopping Analysis

Biomarker analyses are dependent upon the availability of appropriate biomarker assays and may be deferred or not performed if, during or at the end of the study, it becomes clear that the analysis will have no scientific value or if there are not enough samples or responders to allow for adequate biomarker evaluation. In the event the study is terminated early or shows poor clinical efficacy, completion of biomarker assessments will be based on justification and intended utility of the data.

Additional Collections

If it is determined at any time before study completion that additional material is needed from a formalin-fixed, paraffin-embedded tumor sample for the successful completion of the protocol-specified analyses, the sponsor may request that additional material be retrieved from existing samples. Also, based on emerging scientific evidence, the sponsor may request additional material from previously collected tumor samples during or after study completion for

a retrospective analysis. In this case, such analyses would be specific to research related to the study drug or diseases being investigated.

9.7. Palatability Assessment

Palatability of ibrutinib will be measured using a visual analog scale adapted from published literature.^{22,23,39} The scale is a 5-point visual analog scale incorporating a facial hedonic scale designed to span pediatric ages and levels of subject comprehension. Children as young as 4 years should have the developmental capacity to assess palatability using this scale. Assessments will be obtained during the study Treatment Phase as specified in the Time and Events Schedule ([Table 1](#) and [Table 2](#)).

9.8. Safety Evaluations

All subjects who receive at least 1 dose of treatment will be considered evaluable for safety. The SET will monitor subject safety during the dose-confirmation part of the study. Part 2 of the study will be monitored by an independent DMC (details are provided in [Section 11.8](#), Independent Data Monitoring Committee). Subjects will be assessed by physical examination, weight evolution, and performance status evaluation. Hematology and clinical chemistry tests will be performed at regular intervals as specified in the Time and Events Schedule. The study will include the following evaluations of safety and tolerability according to the timepoints provided in the Time and Events Schedule ([Table 1](#), [Table 2](#), [Table 3](#), and [Table 4](#)).

Adverse Events

Adverse events will be reported by the subject (or, when appropriate, by a caregiver, surrogate, or the subject's legally-acceptable representative) from the time of signed consent until 30 days after the last dose of study drug (including ibrutinib monotherapy) or until the start of a subsequent systemic antineoplastic therapy, if earlier, unless the subject has withdrawn consent for study participation. Adverse events occurring after 30 days following the last dose of study treatment should also be reported if considered related to study treatment. Any clinically relevant changes occurring during the study must be recorded on the Adverse Event section of the CRF. Any clinically significant abnormalities persisting at the End-of-Treatment visit/early withdrawal will be followed by the investigator until resolution or until a clinically stable endpoint is reached. All Grade 3 or 4 adverse events considered related to study drug must be followed until recovery to \leq Grade 1 or baseline, deemed irreversible, or until end of study.

All adverse events will be recorded with the details of the duration and the severity of each episode, action taken with respect to the study drug, investigator's evaluation of its relationship to the study drug (ie, not related, doubtful, possibly, probably, very likely related), and the subjects' outcome. All serious adverse events (life-threatening, results in death, results in or prolongs hospitalization, or results in persistent disability/incapacity, congenital anomaly/birth defect, suspected transmission of any infectious agent, or medically important) must be reported to the sponsor within 24 hours. Progressive disease of NHL should not be reported as an adverse event, but instead, the clinical diagnosis that is associated with disease progression is to be reported.

Adverse Events of Special Interest

Major hemorrhage has been identified as an adverse event of special interest and will require enhanced reporting and data collection (see Section [12.3.3](#), Adverse Events of Special Interest, for details).

Clinical Laboratory Tests

Blood samples for serum chemistry and hematology will be collected. Samples for required laboratory tests may be collected on the day of or day before dosing. For Day 1 Cycle 1 only, clinical laboratory tests do not need to be repeated if the Screening tests were performed within 5 days prior to the first dose of study treatment, with the exception of pregnancy testing which needs to be performed within 24 hours prior to the start of treatment per cycle.

The investigator must review the local laboratory results, document this review, and record any clinically relevant changes occurring during the study in the adverse event section of the CRF. For example, laboratory abnormalities leading to an action regarding any study treatment (dose change, temporary stop, delay of the start of a cycle or permanent stop) or the start of concomitant therapy should be reported. For each laboratory abnormality reported as an adverse event, the following laboratory values should be reported in the laboratory section of the electronic CRF: the value indicative of the onset of each toxicity grade; the most abnormal value observed during the adverse event, and the value supporting recovery to Grade ≤ 1 or to baseline values. The following tests will be performed by the local laboratory at the timepoints shown in the Time and Events Schedule ([Table 1](#), [Table 2](#), [Table 3](#), and [Table 4](#)):

- Hematology Panel
 - hemoglobin
 - platelet count
 - white blood cell count
 - absolute neutrophil count
 - absolute lymphocyte count
 - lymphoblasts (also called blasts) if applicable
- Serum Chemistry Panel
 - sodium
 - potassium
 - blood urea nitrogen or urea
 - creatinine
 - aspartate aminotransferase
 - albumin
 - alkaline phosphatase
 - total bilirubin
 - lactic acid dehydrogenase
 - uric acid
 - alanine aminotransferase
- Viral Serology Panel
 - HBsAg
 - HBsAb
 - HBcAb
 - Hepatitis C
 - HIV

If Hepatitis B core antibody is positive, Hepatitis B DNA by polymerase chain reaction (PCR) needs to be performed and confirmed as negative to continue with study participation. Subjects should be monitored for viral reactivation by liver enzymes and Hepatitis B PCR when appropriate and prophylactic antiviral medication should be considered per local practice.

- Tetanus and pneumococcal antibody titers (central laboratory)
- Serum or urine pregnancy testing for young women of childbearing potential only

Electrocardiogram/Echocardiography/MUGA Scan

Baseline LVEF/SF must be assessed by MUGA or echocardiogram and demonstrate LVEF $\geq 50\%$ or SF $> 28\%$ for subjects to be eligible and may be repeated throughout the study, protocol directed or when clinically indicated. When the examination is repeated, the same modality should be used. Echocardiography/MUGA and 12-lead ECGs will be obtained for all subjects at the timepoints specified in the Time and Events Schedule ([Table 1](#), [Table 2](#), and [Table 3](#)). Additional cardiovascular assessments should be performed as clinically appropriate to ensure subject safety.

During the collection of ECGs, subjects should be in a quiet setting without distractions (eg, television, cell phones). Subjects should rest in a supine position for at least 5 minutes before ECG collection and should refrain from talking or moving arms or legs. If blood sampling is scheduled for the same timepoint as ECG recording, the ECG should be performed before the blood draw.

Vital Signs

Assessment of pulse/heart rate and blood pressure is expected at every protocol-specified visit from screening until end of treatment. Blood pressure and pulse/heart rate measurements should be preceded by at least 5 minutes of rest in a quiet setting without distractions (eg, television, cell phones). Clinically significant abnormalities should be recorded as adverse events. If an abnormal heart rhythm is suspected, further investigation (ECG and/or Holter monitor) is required per investigator's discretion.

Body Surface Area

Calculation of BSA ([Attachment 3](#)) at Cycle 1 Day 1 is required for CIT and ibrutinib dosing. The BSA should be recalculated if a subject experiences a $> 10\%$ change in weight from the weight used in the most recent BSA calculation. Weight will be collected as specified in the Time and Events Schedule ([Table 1](#), [Table 2](#), and [Table 3](#)).

Physical Examination

Complete physical examination will be performed at Screening. The Screening physical examination will include, at a minimum, the general appearance of the subject, height and weight, examination of the skin, ears, nose, throat, lungs, heart, abdomen, extremities, musculoskeletal system, lymphatic system, and nervous system. Directed physical examination

(includes all organ systems that were previously abnormal or involved with disease and documentation of any clinically relevant abnormalities in any organ) will be performed at the timepoints specified in the Time and Events Schedule ([Table 1](#), [Table 2](#), [Table 3](#), and [Table 4](#)). Lymphoma symptoms reported at Screening should be reviewed and recorded during the directed physical examination.

9.9. Sample Collection and Handling

The actual dates and times of sample collection must be recorded in the CRF or laboratory requisition form. Refer to the Time and Events Schedule for the timing and frequency of all sample collections ([Table 1](#), [Table 2](#), [Table 3](#), and [Table 4](#)). Instructions for the collection, handling, storage, and shipment of samples are found in the Laboratory Manual that will be provided.

Any volume of blood collected must be consistent with the recommendations of the European Medicines Agency (EMA) for study-related blood loss.¹² In pediatric populations this should be no more than 3% of the total blood volume during a 4-week period and not more than 1% of total blood volume at a single timepoint. At a total blood volume estimated at 80 to 90 mL/kg body weight this equals 2.4 to 2.7 mL of blood per kilogram of body weight every 4 weeks or 0.8 to 0.9 mL per kilogram at any one time. It is the responsibility of the investigator to comply with these guidelines and to prioritize study blood collection as follows:

1. Safety laboratory studies (hematology and serum chemistry) that are study-related and not part of routine care
2. Pharmacokinetic samples
3. Pharmacodynamic samples
4. Biomarker samples

10. SUBJECT COMPLETION/DISCONTINUATION OF STUDY TREATMENT/ WITHDRAWAL FROM THE STUDY

10.1. Completion

A subject will be considered to have completed the study if he or she has died before the end of the study, has not been lost to follow-up, or has not withdrawn consent before the end of study.

10.2. Discontinuation of Study Treatment/Withdrawal from the Study

Subjects who discontinue any component of CIT without disease progression will continue study drug (ibrutinib) and remaining components until 3 cycles are completed followed by ibrutinib monotherapy in case of response (PR or better), or until disease progression, or unacceptable toxicity, or until initiating subsequent antilymphoma therapy or a conditioning regimen for stem cell transplant, or for a maximum of three 28-day cycles, whichever occurs first. If study drug is discontinued for any reason, any remaining study treatment (CIT) may continue. Investigators are encouraged to keep a subject experiencing clinical benefit (ie, PR, CR, MR, or NR) in the study unless significant toxicity puts the subject at risk or routine noncompliance puts the study outcomes at risk.

Discontinuation of Study Treatment

A subject will not be automatically withdrawn from the study if they have to discontinue treatment before the end of the treatment regimen. A subject's study treatment will be discontinued if:

- The subject experiences disease progression or relapse
- The investigator believes that for safety reasons or tolerability reasons (eg, adverse event) it is in the best interest of the subject to discontinue study treatment
- The subject becomes pregnant
- The subject or legally authorized representative refuses further treatment
- The criteria for discontinuation of study treatment described in Section 6.2 are met
- A serious protocol violation has occurred, as determined by the principal investigator or the sponsor

If a subject discontinues study treatment for any reason before the end of the Treatment Phase, end-of-treatment and posttreatment assessments should be obtained and scheduled assessments should be continued.

Withdrawal from the Study

A subject will be withdrawn from the study for any of the following reasons:

- Lost to follow-up
- Withdrawal of consent
- Sponsor discontinues the study

If a subject is lost to follow-up, every reasonable effort must be made by the study-site personnel to contact the subject and determine the reason for discontinuation/withdrawal. The measures taken to follow-up must be documented.

When a subject withdraws before completing the study, the reason for withdrawal is to be documented in the CRF and in the source document. Study drug assigned to the withdrawn subject may not be assigned to another subject. Subjects who withdraw will not be replaced. If a subject withdraws from the study, end-of-treatment and posttreatment assessments should be obtained, if possible.

10.3. Withdrawal From the Use of Research Samples

Withdrawal From the Use of Samples in Future Research

The subject may withdraw consent for use of samples for research (refer to Section 16.2.5, Long-Term Retention of Samples for Additional Future Research). In such a case, samples will be destroyed after they are no longer needed for the clinical study. Details of the sample retention for research are presented in the ICF.

11. STATISTICAL METHODS

Statistical analysis will be done by the sponsor or under the authority of the sponsor. A general description of the statistical methods to be used to analyze the efficacy and safety data is outlined below. Specific details will be provided in the Statistical Analysis Plan.

All statistical testing will be performed using a 2-sided test at the 10% level of significance, unless otherwise noted. Confidence intervals will be presented as 2-sided 90% confidence intervals. Summary statistics for continuous variables include mean, standard deviation, median, minimum, and maximum unless otherwise specified. Categorical data will be presented as frequencies and percentages.

11.1. Subject Information

The intent-to-treat (ITT) Population will consist of all randomized subjects where subjects will be analyzed based on randomization, regardless of study drug received. The ITT population will be used for all efficacy analyses. The primary efficacy analysis is based on the ITT population for data collected in the Part 2. Efficacy for Part 1 will be provided as a secondary endpoint for Part 1.

The Safety population will consist of all subjects who received at least 1 dose of treatment. The safety population will be used for all safety analyses and subjects will be analyzed based on actual study drug received.

Summaries (demographics and baseline characteristics, safety) will be presented for Part 1 and Part 2 of the study. Analyses of disposition, demographic, baseline disease characteristics, and prior and concomitant therapy will be conducted on the ITT population. Analyses on treatment compliance and extent of exposure will be conducted on the Safety population. No statistical testing is planned.

Unless otherwise specified, all continuous endpoints will be summarized using descriptive statistics, which will include the number of subjects with a valid measurement (n), mean, standard deviation, median, minimum, and maximum. All categorical endpoints will be summarized using frequencies and percentages. Percentages will be calculated by dividing the number of subjects with the characteristic of interest by the number of subjects in the analysis population or the evaluable population.

11.2. Sample Size Determination

Approximately 72 subjects will be randomized in Part 2. The sample size calculation for the randomized part (Part 2) is based on the assumption of 100% improvement (hazard ratio = 0.5) in median EFS in subjects receiving ibrutinib plus CIT (RICE or RVICI) compared with CIT (RICE or RVICI) (10 months versus 5 months). Utilizing a 2:1 randomization, this study will enroll approximately 72 subjects (approximately 48 subjects treated with ibrutinib [and RICE or RVICI background therapy]) during Part 2. Based on a total of 60 events for the 2 treatment groups, this study will have at least 80% power, given a 1-sided alpha of 0.05. An accrual rate of 1.44 subjects per month will result in a study duration of approximately 4.2 years.

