1.1. Mature B-cell Non-Hodgkin Lymphoma

In children, mature B-cell non-Hodgkin lymphomas (NHLs) occur rarely; the most common types are Burkitt lymphoma (BL) and diffuse large B-cell lymphoma (DLBCL).^{24,29} Although these are aggressive lymphomas that are fatal in weeks to months if untreated,⁸ the cure rate in children with BL and DLBCL is between 85% to 90% after initial treatment.^{25,33} Given this high cure rate, the incidence of relapsed or refractory BL and DLBCL within the broader pediatric population of NHL is very small.^{2,4,6,13,31,35,41} Relapse of pediatric BL most commonly occurs within 6 months of the end of treatment and has a poor prognosis.²⁶ A review of children with mature B-cell NHL who relapsed or progressed following treatment with frontline pediatric B-cell NHL protocols had survival rates of less than 20%; however, these data were not summarized by the individual subtypes of BL or DLBCL.^{3,7,34} Despite the reported overall response rate (ORR) of over 50% in most of these series, the overall mortality of this population is high and the 1- and 2-year event-free survival (EFS) rates are approximately 40% and 20%, respectively. Long-term survival beyond 2 years is poor, with only 10% to 20% of these patients surviving,^{3,13,15,18} underscoring the unmet medical need in this patient population.

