1.4. Background Chemoimmunotherapy

Ibrutinib is being evaluated as add-on therapy to RICE or RVICI (see Table 5 and Table 6, respectively, for doses). In this study, dexamethasone was added to RICE to align with the dexamethasone given as part of RVICI. In a Children's Oncology Group study of children with NHL in the relapsed/refractory setting, RICE led to a 60% ORR.¹⁵ The RVICI regimen has demonstrated a 63% 4-year survival.⁴² For both regimens, triple intrathecal therapy consisting of methotrexate, corticosteroid, and cytarabine will be administered for central nervous system (CNS) prophylaxis in age-appropriate dosing (see Attachment 6). Subjects with CNS disease will receive additional doses of triple intrathecal therapy as per the Time and Events Schedule (Table 5 and Table 6). For further information regarding background therapy, please refer to the local prescribing information.

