9.1.4. Posttreatment Phase (Follow-Up)

After the completion of the End-of-Treatment procedures, all subjects will enter a Posttreatment Phase. During the Posttreatment Phase, subjects randomized to ibrutinib having a response of PR or better after 3 cycles of combination treatment will continue on ibrutinib monotherapy at the same daily dose for three 28-day cycles or until disease progression or unacceptable toxicity, or up until initiating subsequent antilymphoma therapy or a conditioning regimen for stem cell transplantation, whichever occurs first.

For subjects who enter the Posttreatment Phase without disease progression, follow-up visits to assess disease progression will be completed as per [Table 3](#) and [Table 4](#) until PD, the clinical cutoff for the primary endpoint, or for up to 3 years after the date of Cycle 1 Day 1, whichever occurs first. After that, evaluations may be performed as clinically indicated at the discretion of the investigator. After the last protocol efficacy assessment at 3 years, subjects without PD will be followed for survival status as per the standard routine of care of the investigator site. If PD is assessed after 3 years, the date and reason for progression will be entered in the CRF. Additionally, if the investigator becomes aware of the subject death, the date of death will be entered in the CRF.

The interval between follow-up visits should be maintained as outlined in the Times and Events Schedules ([Table 3](#) and [Table 4](#)); if a visit occurs earlier or later than the scheduled visit date, then the next visit date should be rescheduled to maintain the required interval from the previous

visit. At any visit, if there is clinical evidence or suspicion of PD, then appropriate testing must be performed to document progression (See Section 9.2.1).

Investigators may re-contact the subject to obtain long-term follow-up information regarding the subject's safety or survival status as noted in the ICF (refer to Section 16.2.3, Informed Consent and Assent Form). Survival follow-up (physician visit or telephone contact) will be required every 4 weeks for all subjects following PD until death or study end, whichever occurs first. The interval between post-PD survival follow-up visits should be maintained at 4 weeks; if a visit occurs earlier or later than the scheduled visit date, then the next visit date should be rescheduled to maintain the required interval from the previous visit.

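### The 5-versus-10-month, HR 0.5 design does not fit the protocol's own 40% and 20% EFS, and 60 events are not expected at the stated 50 months

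*Protocol*

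**What the plan says.** Protocol 11.2, repeated in the Synopsis and SAP 1.4, sizes Part 2 on "100% improvement (hazard ratio = 0.5) in median EFS" ("10 months versus 5 months"), with 72 subjects randomized 2:1 and accrual of 1.44 per month over about 4.2 years. On power it says: "Based on a total of 60 events for the 2 treatment groups, this study will have at least 80% power". The test level is 1-sided 0.05. Table 11 (SAP Table 2) puts the interim analysis at 30 events and 32 months, and the final analysis at 60 events and 50 months.

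For the same population, Protocol 1.1 reports that "the 1- and 2-year event-free survival (EFS) rates are approximately 40% and 20%, respectively", and that only 10% to 20% survive long term beyond 2 years. Protocol 9.1.5 triggers the final analysis by event count. Protocol 9.1.4 schedules progression visits until progression, the clinical cutoff, or "for up to 3 years after the date of Cycle 1 Day 1". Later evaluation is at the investigator's discretion, and any progression then found is recorded.

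Neither document explains the 5-month control median beside the 40% and 20% rates.

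**The concern.** Pairing a median ratio of 2 with a hazard ratio of 0.5 is the exponential model, and that model reproduces the interim timing in Table 11. Under it, the assumed control arm does far worse than the protocol's background says such patients do. The cited rates correspond to a control median close to the one assumed for the ibrutinib arm.

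If the background rates are nearer the truth, events accrue more slowly than planned. The 4.2-year duration and the power available at that date are then both too favourable. Protocol 3.2 calls this an adequately powered registration study, so a reader needs to know what 72 subjects could deliver under the protocol's own figures.

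**Working it through.** **Inputs.** From Protocol 11.2: HR 0.5, 2:1 allocation (24 control, 48 ibrutinib), 1-sided alpha 0.05, 60 events, 1.44 subjects per month. Accrual lasts 72/1.44 = 50 months, so it fills the whole planned duration. From Protocol 1.1: EFS of 40% at 12 months and 20% at 24 months. From Protocol 9.1.4: 3 years of scheduled assessments. No dropout rate is stated, so none is used.

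**Stated power.** Power = Φ(ln 2 × √(D × 2/9) − 1.645). For D = 60: 0.6931 × 3.651 − 1.645 = 0.886, so power is 81.2%. The plan's figure is reproduced; 80% needs 58 events.

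**Plan's timing.** With uniform accrual up to time T, the expected event fraction for hazard λ is 1 − (1 − e^(−λT))/(λT). Hazards are ln 2/5 = 0.1386 and ln 2/10 = 0.0693 per month.

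- Month 32 (46 subjects): 11.9 control + 18.4 ibrutinib = 30.3 events. This matches Table 11, so the plan's model is evidently exponential.
- Month 50 (72 subjects): 24 × 0.856 + 48 × 0.720 = 20.5 + 34.6 = 55.1 events, power 78.3%. Sixty events are expected at about month 54.

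**Fit to the background.** A 5-month exponential median gives 2^(−12/5) = 18.9% at 1 year and 2^(−24/5) = 3.6% at 2 years. Working back, 40% at 12 months implies a median of 12 × ln 2/(−ln 0.4) = 9.1 months. Likewise 20% at 24 months implies 24 × ln 2/(−ln 0.2) = 10.3 months.

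**Events under the cited rates.** Control follows S(t) and ibrutinib S(t)^0.5. The piecewise curve has constant hazard to month 12, and a second constant hazard from then on. The plateau curves flatten at 20% from month 24, or at 10% from month 36.

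| Control curve | Events (power) at month 50 | All 72 counted to 36 months only | Month of 60th event, no cap |
|---|---|---|---|
| Exponential, 5-month median (plan) | 55.1 (78.3%) | 67.9 (85.2%) | 54 |
| Exponential through 40% at 1 year | 44.4 (70.3%) | 58.3 (80.2%) | 69 |
| Exponential through 20% at 2 years | 41.8 (68.0%) | 55.5 (78.5%) | 74 |
| Piecewise through both | 42.0 (68.2%) | 54.4 (77.8%) | 76 |
| Piecewise, 10% plateau | 41.1 (67.3%) | 54.4 (77.8%) | never |
| Piecewise, 20% plateau | 37.5 (63.9%) | 45.7 (71.4%) | never |

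The 36-month column can be checked by hand. Piecewise through both reaches 10% at month 36: 24 × 0.9 + 48 × (1 − √0.1) = 21.6 + 32.8 = 54.4. With the 20% plateau: 24 × 0.8 + 48 × (1 − √0.2) = 19.2 + 26.5 = 45.7. In the two plateau rows these are also the maximum at any time.

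**The case against.** **The power sentence is true.** Power depends on events and the hazard ratio, not on the control median. A reader might infer that the 80% claim is wrong; it is not. It is conditional on 60 events, and what lacks support is reaching 60 at the stated date.

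**A 5-month median alone does not contradict 40% and 20%.** The trial counts lack of CR or PR after 3 cycles as an event, and Protocol 1.2 reports a 60% response rate on RICE. A curve with 60% at 3 months, 50% at 5, 40% at 12 and 20% at 24 meets every figure. This stands. But on that curve HR 0.5 puts the ibrutinib median at about 20 months, not 10, and month 50 still yields only 43.4 events (69.4%). The median is rescued; the package and its timing are not.

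**The benchmark may be too favourable.** In the RICE study in Protocol 1.2, 3 of 20 subjects (15%) survived beyond 24 months, and EFS cannot exceed survival. Curves through 60% at 3 months and 10% to 15% at 24 months have medians of 5.1 to 5.8 months, close to the assumed 5. They give about 42 to 50 events (68% to 75%) at month 50, depending on the tail. The shortfall shrinks but remains.

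**The trial is event-driven.** A reader might infer that 60 events could never be reached. The documents do not establish that. Without a plateau they arrive late. Three years is not an absolute stop either: Protocol 9.1.4 records later progression and known deaths, and 9.2.5 states no 3-year limit. Nor do the documents state an event-free plateau; the 10% to 20% in Protocol 1.1 is survival.

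**The RVICI figure is not evidence here.** Protocol 1.4 says that "The RVICI regimen has demonstrated a 63% 4-year survival". That is survival, not EFS, and no calculation above uses it.

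**Practical effect is limited.** Enrolment stopped after the interim futility boundary was reached at 31 events (Protocol 11.9.1), so no recruitment decision can change.

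**Conclusion.** The point holds as a mismatch between the sample-size package and the protocol's own background rates, and as an error in expected timing. Sixty events are not expected at month 50 under any curve examined. About 5 of the missing events (60 − 55.1) arise under the plan's own medians; the rest of the gap comes from the cited rates.

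If counting stops at 3 years per subject, the cited rates give 54 to 58 events (78% to 80%) without a plateau, a marginal miss. A 10% to 20% event-free plateau caps the total at 46 to 54 events (71% to 78%).

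These results rest on uniform accrual, no dropout, proportional hazards at HR 0.5, and cited EFS defined comparably to the trial's. The documents do not confirm the last of these. The plateau rows add an assumption of their own.

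**What to change.** In Protocol 11.2 and Table 11, and in SAP 1.4 and Table 2, with the Synopsis aligned:

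- Justify the 5-month control median against the 40% and 20% rates in Protocol 1.1, including whether those rates count non-response after 3 cycles as an event.
- Correct the expected timing of 60 events; on the plan's own medians it is about month 54.
- Give expected events, timing and power under both the 5-month assumption and the cited rates, with and without counting events beyond 3 years.
- State that 80% power is conditional on reaching 60 events.

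The cost is wording and a less favourable stated power at the planned date. It needs no additional enrolment and leaves the analysis method unchanged.
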